6.4 Cross-over

Some scoliosis curves will progress despite brace treatment. The spinal team and orthotist in each centre will be aware that this is monitored by the DMEC for each brace type. Cross-over from NTB to FTB will be discouraged and monitored.

The risk of curve progression reduces after peak height velocity (40) and most patients will be beyond this before progression is noted. Instead, high compliance with the NTB will be encouraged.

Switching will not be permitted from FTB to NTB as this treatment is not currently available on the NHS. If patients wish to switch from NTB to FTB, they will be asked for their reasons why.

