6.5 Other Treatments

Patients will we allowed to have other care such as physiotherapy but this will be recorded. Surgical treatment will not be offered unless the curve gets to 50 degrees as determined by the Radiographic Adjudication Committee (RAC).

7. Randomisation and enrolment

Once eligibility has been confirmed, consent acquired and baseline data taken the participant will be randomly allocated to either the treatment arm (NTB) or the control arm (FTB) on a 1:1 basis, using a web-based system provided by the Sheffield Clinical

Trials Research Unit (CTRU). Patient details (ID, date of birth and stratification information) will be entered into the randomisation system and the treatment allocation will be returned. Randomisation will be completed using minimisation based on site, skeletal maturity (Risser score 0, 1 or 2, and curve size (20-30, 31-40 degrees). Randomisation will be done by site staff. Patients and their parents will be informed of their trial allocation, confirmed by SMS or email, followed by a letter. Their GP will also be informed of their participation in the trial, and their treatment allocation.

8. Outcomes

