of spinal patients currently used to evaluate surgical patients and is familiar to the clinical staff in each centre, and an efficient means of follow-up in routine use. The central team will ensure data quality and data completeness is optimised.

Data Management (CRF design, data cleaning and validation) will be provided by the CTRU. Project-specific procedures for data management will be detailed in a data management plan.

Data will be collected in three phases:

Phase 1: Pre-skeletal maturity

Whilst in brace, patients will be seen routinely every 6-months for clinical monitoring, anchored from the date of randomisation. Routinely collected out-of-brace spinal radiographs will be taken at each visit in order to measure the Cobb angle (primary outcome). This is accepted as best practice guidelines for bracing in AIS (49). Such radiographs will be sent through the Image Exchange Portal and clinical data entered onto the BSR by research staff. Before the 6 month visit, parents and/or patients will be emailed a link to the questionnaires in the BSR which would be labelled for either 'patient' or 'parent' completion. If not completed, they will use a computer or tablet in the clinic to complete the questionnaires, with paper forms available as a back-up. Questionnaire completion will be checked and chased by mail or telephone as required.

There are a few scenarios:

- If the primary outcome is reached (progression to 50 degrees) before skeletal maturity, follow up will continue via email link to the BSR which will collect PROMs every 6 months
- If the patient has surgery, radiographs and questionnaires will be collected at routine post-operative clinic follow-up at 6-8 weeks, 1 year and 2 years after surgery.
- If the patient changes from NTB to FTB (cross-over), the reason will be recorded. Cross-over in the other direction is not allowed. Follow-up will continue unchanged.
- If the patient stops bracing altogether, follow-up will be continued.
- Rarely, during follow-up, patients will develop symptoms that prompt a spinal MRI scan. If this shows spinal dysraphism (dilated central canal is not defined as spinal dysraphism) as the cause for their scoliosis, the patient will continue in the trial for analysis on 'intention to treat' (ITT) but will be excluded from the per protocol (PP) analysis.

Phase 2: Post-skeletal maturity

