11.1 Sample size

In the BrAIST trial 28% of braced patients progressed to 50 degrees or more before skeletal maturity, which was the primary endpoint (5), so assuming this for the FTB group, with a non-inferiority margin of 11%, 90% power, 2.5% one-sided significance level and 10% attrition, the study will require 780 participants (390 per group).

This margin was chosen based on participants and parents. They have stated there is considerable functional and psychological benefit from not wearing braces during the daytime. During both PPI focus groups patients have expressed mixed views about FTB, which some were being treated with, and the concept of NTB. Approximately 50% of the group expressed a preference for a NTB. In our SAUK survey, 60% said

they would prefer a NTB compared to 27% for a FTB (and 7% no brace, 6% no answer).

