11.2 Statistical Analysis

The trial will be analysed and reported according to CONSORT guidelines for noninferiority designs (54).

The ITT population (and safety) populations will consist of all participants who consent and are randomised to receive FTB or NTB.

The per protocol (PP) will be defined for participants in the FTB group, as

receiving the FTB treatment as documented in the study protocol (see Section 6)
 Complying and adhering to the treatment they were assigned to. Compliance with FTB would mean wearing the brace for average of >12.9hrs/day (= >65% of the minimum prescribed time) over the post-randomisation follow-up period.

For the NTB group, the PP population will be defined as

1) receiving the NTB treatment as documented in the study protocol

2) Complying and adhering to the treatment they were assigned to. Compliance with NTB would mean wearing the brace for average of >5.2hrs/day (= >65% of the minimum prescribed time) over the post-randomisation follow-up period.

Patients who cross-over from NTB to FTB will be removed from the PP population for the analysis of the primary outcome.

The binary primary outcome is curve progression to 50 degrees or more (treatment failure) before skeletal maturity and skeletal maturity without this degree of curve progression (treatment success). Non-inferiority for the primary outcome will be declared if the two-sided 95% confidence interval (equivalent to a one-sided 97.5%) for the risk difference in the event rate of progression to 50 degrees between the NTB group and the FTB group does not exceed 11%. The analysis will be completed using a Generalized Linear Model (GLM) with binomially distributed response and identity link (55) adjusted for baseline covariates (site, skeletal maturity Risser score 0, 1 or 2, and Cobb angle). This will be conducted on both an intention-to-treat (ITT) population and per protocol (PP) basis. The adjusted differences in failure rates, along with 95% con-fidence intervals will be calculated and presented.

Missing data

For the primary outcome, curve progression to 50 degrees or more (treatment failure) and skeletal maturity without this degree of curve progression (treatment success) any missing outcome data will be imputed through a default "worst" case scenario (i.e. assume treatment failure) and "best" case scenario (i.e. assume treatment success) and the results compared with the available data analysis.

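### The primary non-inferiority analysis does not say which missing-data result decides, and none of its three versions uses the recorded Cobb angle and Risser stage of children lost before an outcome

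*Protocol*

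**What the plan says.** Protocol 11.2 defines an ITT population that "will consist of all participants who consent and are randomised to receive FTB or NTB". The primary analysis is a binomial identity-link model on one final binary outcome, adjusted for site, Risser score and Cobb angle as baseline covariates. Non-inferiority requires the 95% confidence interval for the risk difference to stay within 11 points.

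The missing-data paragraph of 11.2 gives two scenarios for missing final outcomes, all failure and all success, with "the results compared with the available data analysis". The word default stands beside the all-failure scenario. No sentence says which of the three results decides.

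Section 9 (Phase 1) provides interim data: "Routinely collected out-of-brace spinal radiographs will be taken at each visit in order to measure the Cobb angle (primary outcome". Visits are every 6 months, and the schedule in 9.1 lists Risser stage with Cobb angle at the same visits.

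Later in 11.2 the protocol plans a time-to-event analysis of the primary outcome and a longitudinal mixed model for Cobb angle. It also plans inverse probability weighting for non-adherence and cross-over, because excluding such children may depend on prognosis. No comparable step is given for missing primary outcomes.

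**The concern.** A child last measured at 47 degrees and a child last measured at 22 degrees have very different chances of reaching 50. Each of the three planned versions of the primary analysis treats them alike: both dropped, both failures, or both successes. Prognostic information that the trial already collects plays no part in the non-inferiority decision.

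In a non-inferiority trial this can matter in the unsafe direction. If progressing NTB children were lost more readily than progressing FTB children, the observed NTB failure rate would be too low and the difference would shrink towards non-inferiority. Setting missing outcomes to the same value in both arms does not necessarily guard against this, because with equal loss it also pulls the arms together. Agreement among the three results could then be read as robustness when it is not. Because no deciding analysis is named, a disagreement among them would also have no agreed resolution.

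**Working it through.** **Plan's own figure.** Inputs from Protocol 11.1: "In the BrAIST trial 28% of braced patients progressed to 50 degrees or more before skeletal maturity"; design "with a non-inferiority margin of 11%, 90% power, 2.5% one-sided significance level and 10% attrition"; result "the study will require 780 participants (390 per group". Allocation is 1:1 (section 7).

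n per arm = (1.960 + 1.282)² × 2 × 0.28 × 0.72 / 0.11² = 350.1, rounded up to 351. Then 351 / 0.9 = 390 per arm, 780 in total. Reproduced.

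**Set-up for the check.** True rates are placed at the margin (FTB 28%, NTB 39%), so any claim of non-inferiority is false and the nominal rate is 2.5%.

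- d = share of NTB outcomes missing; x = true failure risk among missing NTB children.
- FTB loss is unrelated to outcome, so the observed FTB rate stays at 0.28.
- Observed NTB rate = (0.39 − d·x)/(1 − d).
- P(claim) = Φ((0.11 − observed difference)/SE − 1.96), with unpooled SE.

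The 10% attrition is the protocol's. The value of x, the split of loss between arms and the FTB assumption are not in the protocol, so ranges are shown.

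**Worked case: 10% missing per arm, x = 0.60.**
- Observed NTB rate = (0.39 − 0.06)/0.9 = 0.3667; difference = 8.7 points.
- SE with 351 per arm = √(0.3667 × 0.6333/351 + 0.28 × 0.72/351) = 0.0352.
- P(claim) = Φ(0.0233/0.0352 − 1.96) = 9.7%.
- All failure: NTB 0.33 + 0.10 = 0.43, FTB 0.252 + 0.10 = 0.352; difference 7.8 points; P(claim) 14.9%.
- All success: NTB 0.33, FTB 0.252; difference 7.8 points; P(claim) 16.5%.

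With equal 10% loss, both scenarios multiply the available-data difference by 0.9.

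**Range, 10% missing per arm.**

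| x | Available-data difference | Available data | All failure | All success |
|---|---|---|---|---|
| 0.39 (loss unrelated to outcome) | 11.0 | 2.5% | 5.0% | 5.2% |
| 0.50 | 9.8 | 5.3% | 9.2% | 10.0% |
| 0.60 | 8.7 | 9.7% | 14.9% | 16.5% |
| 0.80 | 6.4 | 25.6% | 32.2% | 36.7% |

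In 200,000 simulated trials, all three versions agreed on a false claim in 8.2% (x = 0.60) and 22.1% (x = 0.80).

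**Less loss, 5% per arm.** Available data: 5.1% (x = 0.60) and 9.2% (x = 0.80).

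**More loss in NTB, 15% against 5%.** Available data: 18.3% (x = 0.60) and 55.2% (x = 0.80). All failure: 0.4% and 3.7%, so here that scenario does protect. All success: 65.5% and 91.7%.

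**Other directions, 10% missing per arm.**
- Lost children at 60% risk in both arms: observed rates 36.7% and (0.28 − 0.06)/0.9 = 24.4%; difference 12.2 points; false claims about 1%.
- Lost children at 60% risk in FTB only: 39% − 24.4% = 14.6 points; false claims about 0.1%.

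Both of these are conservative.

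**The case against.** The strongest reply has four parts.

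**The protocol does not call available data its main analysis.** This stands. A reader might infer it because the two imputed results are compared against it, but no sentence says so, the word default belongs to the all-failure scenario, and ITT covers everyone randomised. What can be said is that the deciding analysis is unnamed.

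**The interim readings are used.** This also stands. A reader might infer that no planned analysis uses them for children who leave early. Section 11.2 contradicts that: the mixed model takes Cobb angle at all available time points, on a non-inferiority basis, and the ITT time-to-event analysis retains partial follow-up. Both are secondary or additional, however, and the 11-point rule is attached to the binary model.

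**One-sided loss is not shown.** A reader might take "Cross-over from NTB to FTB will be discouraged and monitored" (section 6.4) to mean that families of progressing NTB children must leave the trial to obtain an FTB. The documents do not support that. Cross-over is discouraged but allowed, and follow-up continues after it and after bracing stops (section 9). Withdrawing patients may let routine data inform the primary outcome (9.6). A reading above 45 degrees triggers central review (8.1), and surgery depends on a central reading of 50 (6.5), so a progressing child has reason to stay in clinic. FTB families may also leave: 60% of those surveyed preferred an NTB (11.1). The direction of any bias is therefore unknown.

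**An imputation model belongs in the SAP.** As to detail, yes. But the protocol does more than defer: it states a method for missing primary outcomes, and the point concerns that stated method.

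**Conclusion.** The point holds in limited form. Section 11.2 fixes a crude method for missing primary outcomes, leaves the deciding result unnamed, and uses none of the recorded 6-monthly Cobb and Risser readings in the decision.

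The size depends on assumptions the protocol neither states nor excludes. If loss is related to progression in NTB only, at 10% per arm, the available-data type I error is about 5% to 26% for x between 0.50 and 0.80. Equal loss makes the all-failure and all-success results worse, not safer. The all-failure scenario protects only when NTB loses clearly more children. Equally informative loss, or informative loss in FTB alone, gives a conservative available-data result. A child already recorded at 50 degrees or more before loss counts as a failure, so any bias comes only from children lost below 50.

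This is a weakness worth correcting at low cost, not evidence that the trial will reach a false conclusion.

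**What to change.** In 11.2:

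1. Name the ITT analysis that decides non-inferiority.
2. Make it multiple imputation of missing final outcomes for all 780, done separately by arm, from baseline Cobb and Risser, last observed Cobb and Risser, change from baseline, and time since randomisation.
3. Keep the available-data, all-failure and all-success results as sensitivity analyses.
4. Add an arm-specific delta or tipping-point analysis in which missing NTB outcomes are worse than missing FTB outcomes.

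Step 4 is needed because imputation restores the 11-point difference and about 2.5% error only if the recorded readings capture why children were lost. Progression after the last visit is not covered. The full extreme (NTB missing as failure, FTB missing as success) is too harsh to decide on alone: with true rates of 28% in both arms and 10% missing per arm it adds 10 points (35.2% against 25.2%) and leaves 4.9% power.

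Cost: analysis work only. The data are already scheduled and the sample size does not change. The small downside is reliance on an imputation model, which must be fixed before unblinding.

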8.2 Secondary outcomes/endpoints

Patient-reported outcomes (collected throughout the study unless stated otherwise):

- 1. Scoliosis Research Society 22 questionnaire (41);
- 2. Paediatric health related quality of life, measured using the CHU9D (42);
- 3. Bad Sobernheim Stress Questionnaire (BSSQ) (43), a brace specific questionnaire assessing the psychological effects of bracing;
- 4. Revised Children's Anxiety and Depression Scale (RCADS 25) (44);
- 5. PROMIS Paediatric Sleep Disturbance Short Form 4a (45);
- 6. PROMIS Paediatric Sleep Related Impairment Short Form 4a
- 7. Modified Client Satisfaction with Device module of the Orthotics and Prosthetics Users' Survey (CSD-OPUS) (46)
- Educational information assessed using a bespoke questionnaire after GCSE results;

Parent Questionnaires (collected throughout the study unless stated otherwise):

- 9. Patient Cost Questionnaire, using a bespoke questionnaire
- 10. Resource Use Questionnaire, using a bespoke questionnaire;
- 11. School attendance (only during bracing).

Clinical (collected throughout the study unless stated otherwise):

12. Radiological measures from out-of-brace spinal radiographs (with correction of any leg length inequality): Cobb angle, curve type, curve apex, Risser sign, in-brace

Cobb angle, frontal plane balance, apical vertebral rotation, apical vertebral translation;

- 13. In-brace correction, measured for all new braces as the percentage Cobb angle correction in-brace compared with out-of-brace. The in-brace x-ray will be performed standing for FTB and supine for NTB. This reflects brace quality and curve flexibility. Bracing is more likely to fail when there is a lower initial in-brace correction of the curve (47,48). In-brace correction will be monitored during the trial by the DMEC for the new intervention of the NTB and will feedback any training suggestions to the Trial Management Group (TMG);
- 14. Menarchial age;
- 15. Details of any surgery for scoliosis correction;
- 16. Other treatments prescribed to treat scoliosis, e.g. scoliosis specific exercises;
- 17. Complications (e.g. skin irritation) and Serious Adverse Events;
- Brace compliance, assessed using the implantation of a temperature sensor in the FTB or NTB (collected only during bracing);
- 19. Treatment switching, including reason for doing so (bespoke questionnaire).

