9.1 Study assessments schedule

Data collection will follow the following schedule to the point of surgery (for those patients who have surgery):

	Phase 1 (pre-skeletal maturity)		Phase 2 (2 years post skel- etal maturity)		Phase 3 (long term)	
	Screening	Baseline/ randomisation	Every 6 months, until skeletal ma- turity	12 months post skele- tal maturity	24 monthly post skele- tal maturity	10 years post skele- tal maturity
	CI	inical		-		
Screening form/log (baseline visit)	MN/IP	-	-	-	-	-
Eligibility form	MN	-	-	-	-	-
Informed consent form	E	-	-	-	-	-
Demographics (age, sex, diagnosis, medical history, medication)	MN	-	-	-	-	-
Height, weight	IP	-	IP	IP	IP	-
Cobb angle, Risser stage	MN (pre ra	andomisation)	CT/RAC	CT/RAC	CT/RAC	-
Additional radiological measures (curve type, curve apex etc)	СТ	-	СТ	СТ	СТ	-
Need for surgery	-	-	MN	MN	MN	E
In-brace correction	-	CT (0-6 weeks aft ting		-	-	-
Compliance	-	-	SEN	-	-	-
Treatment switching	-	-	MN	-	-	-
	Patient repo	orted measures				
SRS-22, CHU9D, RCADS 25, PROMIS sleep x2	-	IP/E	IP/E	IP/E	IP/E	E
BSSQ, OPUS CSD (whilst in brace only)	-	IP/E	IP/E	-	-	-
Educational information (summer of year 11)	-	-	E~	E~	E~	E~
Other treatments prescribed to treat scoliosis	-	IP/E	IP/E	IP/E	IP/E	-
	Parent qu	lestionnaires				
Ethnicity	-	E	-	-	-	-
Resource Use Questionnaire	-	E	E	E	E	E#
Patient Cost Questionnaire	-	E	-	-	-	-

School attendance	-	E	E	-	-	-
Harms						
Complications and SAEs	-	-	IP/E	E	E	E

MN = medical notes or BSR form, IP = in-person, RAC = radiographic adjudication committee, E = Electronic, online via an email link sent to the patient (may be chased by mail or telephone), CT = central team, SEN = sensor, implanted into brace. ~ collected summer of year 11, age 16, independent of where the patient is in the study # completed by the patient at 10 years

NB. The screening log will capture the details of any patient who has had the trial discussed with them. This allows capture of information relating to reasons for non-participation, and also dates of contact for reporting in line with CONSORT.

X-rays are intended to be in line with the frequency in standard care, however, it may be that at some centres, a maximum of 4 additional x-rays are undertaken in some patients if their usual care differs.

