Before randomisation, patients will be asked if they have a preference for which brace they would want. This question will be asked by the site research team and documented on the study database, rather than a specific questionnaire.

If patients choose to switch from NTB to FTB, or to stop bracing altogether, a questionnaire will be sent to them to ask for their reasons why. Patients who have surgery will be managed as above whilst on the waiting list but will be followed up with radiographs and questionnaires (SRS-22, CHU9D, RCADS 25, PROMIS sleep x2, resource use questionnaire and school attendance) at 6-8 weeks, 1 year and 2 years after surgery, with a plan for 10 year follow-up. Educational information, other treatments, complications and SAEs will be recorded. Patients having surgery after skeletal maturity will only have follow-up to 1 year.

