The primary CE analyses will take an NHS and personal social services perspective in accordance with NICE (59), and the primary cost per QALY analysis will take a lifetime perspective, with proportions of patients who do and do not progress to surgery estimated based upon scoliosis degrees. A secondary analysis will present cost per QALY results restricted to the trial follow-up period. Intervention costs will be based upon information collected using CRFs, to include the type of brace and the resource use associated with fitting it. Wider resource use will include any other health care costs incurred (such as primary care appointments, and hospital admissions or appointments) that are related to the brace or scoliosis. Information on these will be collected via a bespoke resource use questionnaire. Unit costs will be derived from national sources (60,61). Health related quality of life (HRQL) will be estimated using the CHU9D questionnaire (42), specifically developed for children aged between 7 and 17. Both measures can be used to estimate preference-based utility scores, allowing QALYs to be derived. For the evaluation that takes a lifetime perspective we will extrapolate beyond adolescence using utility scores based on a search of the literature. A supplementary analysis from a broader perspective, incorporating societal costs associated with parents' time taken off work and travel costs associated with hospital visits related to the brace or scoliosis, will be included. Information on these costs including on private health care costs associated with the brace or scoliosis will be collected via a patient cost questionnaire.

The primary CE analyses will be based on ITT-based estimates of effectiveness. However, analyses that incorporate findings from the PP analysis and/or analyses that adjust for treatment crossover will be undertaken, if these are deemed relevant given the protocol violations and treatment switches that are observed in the trial, and given the decision problem defined for the economic evaluation; that is, whether initiating treatment with NTB represents a cost-effective use of NHS resources compared to initiating treatment with FTB. Results will allow for uncertainty using bootstrapping and probabilistic sensitivity analysis. Incremental CE ratios will be presented.

12. Ancillary sub-studies

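### The protocol contradicts itself on when the Patient Cost Questionnaire is collected: throughout the study in 8.2, at baseline only in the 9.1 schedule, although 11.2 relies on it for costs that arise during bracing

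*Protocol*

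**What the plan says.** Four places in the protocol bear on the timing of the Patient Cost Questionnaire.

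- **Section 8.2** groups it under the heading "Parent Questionnaires (collected throughout the study unless stated otherwise" and lists it as "Patient Cost Questionnaire, using a bespoke questionnaire", with no timing restriction. Two items further on, school attendance does carry one: "School attendance (only during bracing".
- **Section 9.1, schedule table**, has six columns: screening, baseline/randomisation, every 6 months until maturity, 12 months, 24 months and 10 years after maturity. The Patient Cost Questionnaire has an entry under baseline/randomisation and a dash in the other five columns. The Resource Use Questionnaire, in the row directly above, is marked at baseline and at every follow-up column.
- **Section 9.1, text below the table**, names the questionnaires for patients who have surgery: "SRS-22, CHU9D, RCADS 25, PROMIS sleep x2, resource use questionnaire and school attendance". The Patient Cost Questionnaire is not among them.
- **Section 11.2, Economic evaluation**, plans a supplementary analysis from a broader perspective that adds parents' time off work and travel for hospital visits. It then says: "Information on these costs including on private health care costs associated with the brace or scoliosis will be collected via a patient cost questionnaire".

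**The concern.** The economic section needs costs that build up while a child is in brace, after maturity and, for some, after surgery. The schedule collects the named source once, at a point when no participant can have incurred a brace cost. The omission appears twice, in the table and in the post-surgery list, so it does not look like a single slip in one cell.

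At stake is the supplementary societal analysis. Full-time and night-time bracing could differ in clinic attendance, in parents' lost working time and in privately bought care. A form completed before allocation cannot observe a difference that arises afterwards. An analysis plan written later cannot supply answers that were not collected, so the timing has to be settled in the protocol.

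**Working it through.** The protocol states no number of questionnaire administrations, so there is no figure of its own to reproduce. The check is a comparison of passages and a count.

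**1. Is there a brace at the baseline form?**
- Section 5.2 excludes previous bracing.
- Section 7 takes baseline data before allocation.
- Section 9.2 puts brace measurement at weeks 2-6, after randomisation, and fitting at weeks 4-8.

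So a baseline form can record costs already incurred for scoliosis, but none for a brace.

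**2. Could the table row be a reading error?**
The row has six entries for six columns, as does the Resource Use Questionnaire row above it. A shifted cell is unlikely.

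**3. Administrations after baseline, per participant**

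Inputs: mean time to skeletal maturity of 28 +/- 9 months (Trial Summary, Duration of follow-up), hence 28 - 9 = 19 and 28 + 9 = 37 months; visits every 6 months until maturity; two further time points at 12 and 24 months after maturity (9.1). The 10-year point is left out because section 4 places it under separate approvals. The count is for a participant without surgery.

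Formula if collected throughout: completed 6-monthly visits + 2, where completed visits = months to maturity / 6, rounded down.

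| Months to maturity | 6-monthly visits | Under 8.2 | Under the 9.1 table |
|---|---|---|---|
| 19 | 19/6 = 3.2, so 3 | 3 + 2 = 5 | 0 |
| 28 | 28/6 = 4.7, so 4 | 4 + 2 = 6 | 0 |
| 37 | 37/6 = 6.2, so 6 | 6 + 2 = 8 | 0 |

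For patients who have surgery, the follow-up points in 9.1 are 6-8 weeks, 1 year and 2 years (1 year at most if surgery comes after maturity). The post-surgery list puts the questionnaire at none of them.

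**4. What could still be estimated if the table governs?**

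Write a participant's societal cost over follow-up as

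(number of visits) x (travel and time cost per visit) + (time off work not tied to a counted visit) + (private care).

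- The number of visits can come from the Resource Use Questionnaire, which is collected at every follow-up and after surgery.
- The cost per visit could come from a one-off baseline form, if that form asks for it and the answer is assumed to hold for the years that follow.
- The last two terms have no stated follow-up source, because 11.2 assigns private care to the Patient Cost Questionnaire.

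**The case against.** Three points can be made on the other side.

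**The table may simply be the exception that 8.2 allows for.** The 8.2 heading applies unless something else is stated, and the table does restrict other items that 8.2 leaves open: the BSSQ and the device satisfaction module are limited to time in brace only there. This has some force. But that row carries an explicit note, whereas the Patient Cost Questionnaire row carries none. And even if the table settles the timing, the conflict with its use in 11.2 remains.

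**A one-off form might be enough.** As step 4 shows, unit costs multiplied by visit counts would give arm-specific travel and visit-time costs. Both questionnaires are bespoke and their content is not shown, so this design cannot be ruled out. A reader might infer from the table that the societal analysis would have no post-randomisation data at all and could not compare the arms. The documents do not support that: 8.2 says the opposite of the table, and the Resource Use Questionnaire supplies follow-up counts in either case. What stands is that the protocol nowhere states the unit-cost method, and that the method would not capture brace-related private care.

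**The reach is limited.** Section 11.2 calls this analysis supplementary. The primary cost-effectiveness analyses draw on case report forms, the Resource Use Questionnaire and the CHU9D. Nor does the protocol show how the form was set up in the registry database, so an actual loss of data is not established. All of this stands and limits the weight of the point.

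**Conclusion.** The inconsistency is certain: 8.2, the 9.1 table, the 9.1 post-surgery list and 11.2 do not fit together on the timing of this questionnaire. The consequence is conditional. If the schedule is followed as written, post-baseline administrations are 0, against about 6 per participant under 8.2 (5 to 8 across 19 to 37 months to maturity). Brace-related private costs, and directly observed time and travel costs by arm, would then not be captured for the supplementary societal analysis.

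The count assumes visits at exact 6-month intervals, the quoted mean and spread of time to maturity, no surgery, and no 10-year follow-up. The primary NHS and personal social services analysis, the primary outcome and the sample size are untouched. The point is worth correcting, but it does not threaten the trial's main conclusions.

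**What to change.** Reconcile 8.2, both parts of 9.1, and 11.2 in one of two ways.

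1. **Repeated collection.** Give the Patient Cost Questionnaire the Resource Use Questionnaire's pattern at the 6-monthly visits and at 12 and 24 months after maturity, and add it to the post-surgery list.
2. **One-off form.** If a single baseline unit-cost form is intended, say so in 8.2 and 11.2, state that its unit costs are multiplied by visit counts from the Resource Use Questionnaire, and move the private-care and time-off-work items into the Resource Use Questionnaire so that they are asked at follow-up.

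Either way the cost is a minor amendment and a change to the electronic form schedule or content. The first option also takes a few extra minutes of parents' time at each follow-up. The second keeps most of that burden down but rests on unit costs staying stable over follow-up.
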